### **3.5.3 Other Co-Variates/Control Variables**

Baseline demographics and clinical characteristics will be used in statistical analysis models.

### **3.5.4 Derived Variables**

- Number of consultations/visits to healthcare professionals for treatment of RA, categorized by the treatment department
  - ✓ Family Medicine
  - ✓ Rheumatologist
  - ✓ Gerontologist
  - ✓ Orthopedist
  - ✓ Internist
  - ✓ Emergency department
  - ✓ Traditional Medicine
  - ✓ Rehabilitation Medicine
  - ✓ Other
- Number of procedures received when visiting the healthcare professional(s) for treatment of RA
  - ✓ Chest X-Ray
  - ✓ Spine X-Ray
  - ✓ Neck X-Ray
  - ✓ Shoulder X-Ray
  - ✓ Hand X-Ray
  - ✓ Knee X-Ray
  - ✓ MRI
  - ✓ CT scan
  - ✓ Electrocardiogram
  - ✓ Blood sample taken
  - ✓ Urine test
  - ✓ Endoscopy
  - ✓ Bone scan
  - ✓ Liver function test
  - ✓ Tuberculin Skin Test

- ✓ Sputum tests
- ✓ Other
- Number of surgeries received when visiting the healthcare professional(s) for treatment of RA
  - ✓ Arthroscopy
  - ✓ Carpal tunnel release
  - ✓ Cervical spinal fusion
  - ✓ Total knee replacement
  - ✓ Total hip replacement
  - ✓ Knee arthrodesis (fusion)
  - ✓ Hip arthrodesis (fusion)
  - ✓ Synovectomy
  - ✓ Other
- Number of hospitalizations in relation to RA
- Length of stay: total days in hospital in relation to RA
- Number of concomitant medications taken for RA
- Disease Modifying Antirheumatic Drug (DMARD)
  - ✓ Auranofin (Ridaura, Myochrysine)
  - ✓ Azathioprine (Imuran)
  - ✓ Cyclosporine (Sandimmune and Neoral)
  - ✓ Hydroxychloroquine (Plaquenil)
  - ✓ Leflunomide (Arava)
  - ✓ Methotrexate (Rheumatrex, Folex)
  - ✓ Minocycline (Minocin, Dynacin and Vectrin)
  - ✓ Sulfasalazine (Azulfidine)
  - ✓ Others
- Anti-inflammatory Drug (NSAID)
  - ✓ Ibuprofen (Advil, Motrin, Nuprin)
  - ✓ Naproxen (Naprosyn, Anaprox, Aleve)
  - ✓ Celecoxib (Celebrex)
  - ✓ Aspirin (ASA)
  - ✓ Diclofenac (Voltaren)
  - ✓ Indomethacin (Indocid)
  - ✓ Others
- Others
  - ✓ Steroids

- ✓ Stomach or gastric medications

### **3.5.5 Conventions**

Given the real world nature of the data, multiple imputation methods for missing data will introduce bias as missing data cannot be considered completely at random (MCAR) or at random (MAR). Due to the observational nature of this study, non-imputing process will be applied, except with date data where the exact day is missing; day “15” will be assumed. Efficacy measures are not assessed after a participant discontinues adalimumab. The exception to this will be the analysis of proportion of patients at 24 weeks who remain on adalimumab. Item level data on the PROs will be imputed according to the developers’ recommendations. Therefore, the analysis will be based on available data. The number of patients with missing data for each variable will be summarized and reported.

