9.0 Research Methods

9.1 Study Design

This study is designed as a prospective, observational study to assess the effect of adalimumab on health-related QoL and work productivity in patients with RA in China in clinical practice.

The study population will include Chinese adult patients with a diagnosis of RA who meet the requirements per the local label for treatment with adalimumab at the baseline visit. The decision to prescribe adalimumab for RA should be based on clinical practice criteria without taking participation in this study into account. Patients will be included in the study after a physician's decision of initiating Humira.

Approximately 52 patients diagnosed with RA that meet the inclusion and exclusion criteria will be enrolled at approximately 16 sites.

This study is non-interventional and the subjects/investigator will follow the current clinical practice in each site. Not additional task will be required other than current practice to keep the data as "real world data collect".

The observation period for each patient is 24 weeks. All visits are to be scheduled as per routine clinical practice, regardless of study participation. Patients may discontinue adalimumab treatment or the study at any time without prejudice.

The physician will follow the patient during regular clinic visits at intervals as determined by routine clinical practice. Data at the clinic visits within ± 7 days of the study-defined time points will be collected and data at the clinic visits closest to the study-defined time points will be used for statistical analysis (If there are 2 clinic visits equidistant from a study-defined time point which do not correspond to any other visit, data from the EARLIER clinic visit shall be used for the study-defined time point).

The HAQ DI data will be collected at baseline, Week 12 and Week 24 after treatment initiation with adalimumab, as per standard daily clinical practice. In addition, when available, other PROs of work activity and well-being, including the WPAI, EQ-5D, and SF-36, will also be collected.

The HCRU will also be collected, when available. This includes surgical procedures, hospitalizations, bed days in hospital, physician consultations etc. Costs will be assigned based on the HCRU using standardized costs for each participating countries.

Primary Endpoint

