9.1.1 Study Activities

Table 1 Study Activities (Day 1/Baseline Through 6 months)

	Data Collection/Observation	Baseline ^a	Week 12 (V2) ± 7 days	Week 24 (V3) ± 7 days	Early Termination / Drop out	70 days after the Week 24 or the last dose	150 days after the Week 24 or the last dose
Clinician Packet	Inclusion/exclusion form	X					
	Clinical history/patient demographics	X					
	Comorbidities	X					
	DAS28 (ESR) or DAS28 (CRP)	X	X	X	X		
Patient Packet	EuroQoL 5-Dimension (EQ-5D)	X	X	X	X		
	Short Form 36-Item Health Survey (SF-36)	X	X	X	X		
	Health Assessment Questionnaire (HAQ)	X	X	X	X		
	Work Productivity and Activity Impairment Questionnaire (WPAI)	X	X	X	X		
	Healthcare Resource Utilization (HCRU)	X	X	X	X		
	Patient Global Impression of Change (PGIC)		X	X	X		
	Patient Treatment Satisfaction Questions	X	X	X	X		
Clinical n	Adverse events (including malignancy)	←				→	
	Pregnancy	←					→

a. The Baseline visit date will serve as the reference for all subsequent visits. A \pm 7 day window is permitted around scheduled study visits.

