9.7.8 Safety Analysis

Adverse events occurring while participants are on adalimumab will be coded using Common Terminology Criteria for Adverse Events (CTCAE) classification individually listed by indication groups. The incidences and percentages of individuals experiencing AEs and SAEs within each indication will be summarized by System Organ Class (SOC) with further summaries by severity and relatedness (causality) categories. Adverse events leading to discontinuation and concomitant medications will also be listed and summarized.

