9.7.10 Missing Data

Efficacy measures are not assessed after a participant discontinues adalimumab. The exception to this will be the analysis of proportion of patients at 24 weeks who remain on adalimumab. Item level data on the PROs will be imputed according to the developers’ recommendations. There will be no other imputation for missing data.

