### **3.5.2 Exposure/Independent Variables of Interest**

- **Patient demographics (if data available)**
  - Date of birth
  - Age at baseline
  - Age groups
  - Gender at birth
  - Marital status (married, unmarried)
  - Medical plan type
    - ✓ The type of healthcare plan each patient is enrolled in at baseline will be determined, including National/Public insurance, Private insurance, Employer benefits, and Other
- **Clinical characteristics**
  - Initial Diagnosis of Rheumatoid Arthritis (RA)
    - ✓ Year of initial diagnose
  - Initiation of Adalimumab
    - ✓ First time administration (DD/MM/YYYY)
    - ✓ Dosage of first injection (in mg)
  - Disease status of RA
    - ✓ Moderate (defined as Disease Activity Score in 28 Joints (DAS28) between 3.2 and 5.1)
    - ✓ Severe (DAS28>5.1)
  - Erythrocyte sedimentation rate (ESR) (in mm/hour)
  - C reactive protein (CRP) (in mg/L)
  - Disease Activity Score in 28 joints (DAS28)

To calculate the DAS28, the physician or specialist nurse will:

1. Count the number of swollen joints (out of the 28)

2. Count the number of tender joints (out of the 28)
3. Take blood to measure the erythrocyte sedimentation rate (ESR) or C reactive protein (CRP); the latest measurement in the medical records may also be used if a blood draw is not standard for that visit
4. Ask the patient to make a 'global assessment of health' which will be indicated by marking a 10 cm line between very good and very bad

The physician or specialist nurse will then mark each component score on the CRF and the DAS28 score if calculated (an online scoring calculator for the DAS28 can be found at <http://www.das-score.nl/das28/DAScalculators/dasculators.html>).

The DAS28 will be scored using the following formula:

$$\text{DAS28} = 0.56 * \text{sqrt}(\text{tender28}) + 0.28 * \text{sqrt}(\text{swollen28}) + 0.70 * \ln(\text{ESR or CRP}) + 0.014 * (\text{Global assessment of Health})$$

DAS28 scores will be interpreted using the following categorization:

- ✓ Remission:  $\text{DAS28} \leq 2.6$
  - ✓ Low Disease Activity:  $2.6 < \text{DAS28} \leq 3.2$
  - ✓ Moderate Disease Activity:  $3.2 < \text{DAS28} \leq 5.1$
  - ✓ High Disease Activity:  $\text{DAS28} > 5.1$
- comorbidities
- ✓ Myocardial infarction
  - ✓ Congestive heart failure
  - ✓ Peripheral vascular disease
  - ✓ Cerebrovascular disease
  - ✓ Dementia
  - ✓ Chronic pulmonary disease
  - ✓ Connective tissue disease
  - ✓ Ulcer disease
  - ✓ Mild liver disease
  - ✓ Diabetes

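### The SAP sets any date with a missing day to the 15th, without naming date types or setting bounds, which conflicts with Protocol 9.7.10 and can place an on-treatment event before the first dose

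*SAP*

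**What the plan says.** - **The rule.** SAP 3.5.5 says that a "non-imputing process will be applied, except with date data where the exact day is missing"; the missing day is then taken as the 15th. It lists no date types and sets no limit from any known date. Item-level questionnaire data follow the developers' rules.
- **The protocol on imputation.** Protocol 9.7.10 also allows item-level questionnaire imputation, then adds "There will be no other imputation for missing data". It has no date rule.
- **Where event dates count.** Protocol 9.7.8 restricts the safety summary to events on drug: "Adverse events occurring while participants are on adalimumab will be coded". Protocol 11.4 collects serious events until 70 days after the last dose.
- **Where visit dates count.** Protocol 9.1 says "Data at the clinic visits within ± 7 days of the study-defined time points will be collected" and that "data at the clinic visits closest to the study-defined time points will be used for statistical analysis". The footnote to Table 1 (Protocol 9.1.1) adds "The Baseline visit date will serve as the reference for all subsequent visits".
- **Where discontinuation counts.** SAP 3.5.5 and Protocol 9.7.10 both end efficacy assessment once a patient discontinues adalimumab.
- **What is known exactly.** SAP 3.5.2 has the first administration recorded by day, month and year. A full first-dose date should therefore be available as a bound.

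**The concern.** A mid-month default does little harm where half a month does not matter. It is a poor default where a classification turns on a few days. Suppose adalimumab starts on 20 May and an event after that start is recorded only as May. The rule dates it 15 May, five days before the first dose. The record then shows an order of events that is known to be wrong, and a program that selects events on treatment by date would leave this one out. The loss is one-sided for safety: a genuine on-treatment event disappears from the summary.

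The same wording would reach visit and discontinuation dates, because nothing excludes them. For visits the relevant margin is 7 days. For discontinuation it is the cut-off after which efficacy data are no longer assessed.

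The conflict with Protocol 9.7.10 exists whether or not any partial date occurs. A programmer following the protocol would leave the date missing; one following the SAP would fill it in.

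**Working it through.** Neither document gives a figure to reproduce, and neither says how many dates lack a day. The check therefore counts calendar days and gives rates per affected record.

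**Inputs and assumptions.** Imputed day 15, no bound (SAP 3.5.5). Window of 7 days either side (Protocol 9.1). Month length L from 28 to 31. Assumed, not in the documents: first-dose day f and event day e are independent and uniform over the same month.

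**1. Largest shift.** From day 1 the date moves 15 − 1 = 14 days. From the last day it moves L − 15 = 13 to 16 days. The maximum is 16 days.

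**2. On-treatment events placed before the first dose.** An event is truly on treatment if e ≥ f, which gives L(L+1)/2 day pairs. Imputed to 15, it falls before f only if f > 15, which gives (L−15)(L−14)/2 pairs.

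| L | moved before first dose | true on-treatment pairs | share |
|---|---|---|---|
| 28 | 13×14/2 = 91 | 406 | 22.4% |
| 29 | 14×15/2 = 105 | 435 | 24.1% |
| 30 | 15×16/2 = 120 | 465 | 25.8% |
| 31 | 16×17/2 = 136 | 496 | 27.4% |

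The share is all or nothing for a given patient: every such event if dosing began after the 15th, none otherwise. An event in any other month stays on the correct side of the first dose.

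**3. The opposite error.** An event before the first dose (e < f) gives L(L−1)/2 pairs. It moves onto treatment if f ≤ 15, which gives 0+1+…+14 = 105 pairs. For L = 30 this is 105/435 = 24.1%. Few records should be exposed to it, because collection and treatment both start at baseline.

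**4. Shift against the visit window, if the rule were applied to visits.** The shift exceeds 7 days for true days 1 to 7 and 23 to L, that is 7 + (L − 22) days: 13/28 (46%), 14/29 (48%), 15/30 (50%) or 16/31 (52%).

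**5. Effect of a first-dose bound.** Replace day 15 by the later of the 15th and f when month and year match the first dose. The imputed date can then never precede f, so the shares in step 2 fall to 0%. In return, every same-month pre-treatment onset without a day counts as on treatment (100%, against 23% to 28% under the present rule), unless the record shows the earlier onset.

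**The case against.** The case against is substantial, and most of it limits the size of the point.

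- **No SAP output is affected.** SAP sections 5 and 6 contain no adverse-event analysis or table. This stands. The exposure is in the Protocol 9.7.8 summary, for which SAP 3.5.5 is the only date-imputation convention in either document. That section also does not say that on-drug status is decided from imputed dates.
- **Partial dates may not occur.** Serious events are notified within 24 hours of awareness (Protocol 11.5). Both documents provide for full source review for safety, logic checks and queries (Protocol 9.8.2, SAP 3.3.4). This stands as a reason to expect few. It does not make the count zero: non-serious events arrive only as spontaneous reports (Protocol 11.6), and physicians complete the CRF from medical records (SAP 3.3.2).
- **Protocol 9.7.10 may mean outcome data only.** The sentence follows remarks on efficacy measures and questionnaire items. But it is worded without that limit, and the SAP does not say that it departs from it.

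A reader might go further in three ways that the documents do not support:

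- **That on-treatment events are generally moved before treatment.** This needs three things together: a missing day, an event in the first-dose month, and dosing after the 15th.
- **That pre-treatment events are commonly moved onto treatment.** Consent is taken at baseline, Table 1 starts adverse-event collection there, and adalimumab starts at the same visit. The 24% in step 3 therefore applies to a nearly empty set.
- **That visits are misplaced and the primary HAQ DI result is affected.** Weeks 12 and 24 are prospective, labelled visits whose forms a coordinator checks, and no visit date without a day is shown. An overall misclassification rate for visits also depends on how far visits are assumed to stray from target. In a 30-day month it is 44% for offsets up to 14 days, 35% up to 21 and 26% up to 28. No such figure should be cited as the size of this point.

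**Conclusion.** The point holds as a defect in a stated rule, and it is minor. SAP 3.5.5 is unbounded, does not define its scope, and contradicts the wording of Protocol 9.7.10. Used for adverse-event onset, it would place about 22% to 27% of on-treatment events that fall in the first-dose month and lack a day before the first dose. That range rests on uniform, independent days and is a rate per affected record, not per patient or per event in the study. The 16-day maximum shift needs no distributional assumption. Its consequence for the 7-day window or the discontinuation cut-off is conditional on the rule being applied to those dates, which the SAP neither says nor excludes. With the number of partial dates unknown, no effect on any study result can be calculated.

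It is still worth correcting, because the first-dose date is collected in full and a bound removes an impossible ordering at almost no cost.

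**What to change.** Rewrite the date sentence in SAP 3.5.5 as follows:

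1. Name the dates to which day 15 applies, and limit them to dates where it cannot change a classification. Date of birth is an example: half a month alters age in completed years only when the birth month is the baseline month.
2. For adverse-event and medication onsets in the month and year of first dose, use the later of the 15th and the first-dose date, unless the record shows an earlier onset. Never impute an onset past a known stop date.
3. Exclude visit, questionnaire, dosing and discontinuation dates. Use the recorded visit label and query the site for the day.
4. Amend Protocol 9.7.10 so that it permits this date rule, or state in the SAP that it departs from the protocol and why.

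The cost is one SAP paragraph, a matching protocol sentence and a few lines of code. The statistical downside is the one in step 5: a same-month pre-treatment onset without a day counts as on treatment unless the record shows otherwise. Such events should be rare because collection starts at baseline, and the error is in the conservative direction for safety. The first-dose bound does not repair visit timing, which is why item 3 is needed as well.

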## **4. SAMPLE SIZE AND POWER**

Approximately 100 patients diagnosed with RA will be recruited. The sample size was calculated by assuming an alpha of 0.05 and a power of 0.80 in a two-sided test, resulting in 52 subjects required to recognize a statistically significant improvement in HAQ DI (-0.21) (11). Given the importance of other secondary endpoints, an improvement of 9.9±25 hours of work time lost requires 58 subjects, assuming an alpha of 0.05 and a power of 0.80 in a two-sided test (12). However, since it is expected that approximately half the study population may no longer be working due to their age, approximately twice this number (100 patients) will be required to achieve the required number of respondents. We have also assumed a drop-out rate of 13% (assuming between 10%-15%).

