5.0 Amendments and Updates

Number	Date	Section of Study Protocol	Amendment or Update	Reason
P15-776	05/06/2015	n/a	Initial Protocol	n/a
P15-776	20/08/2015	Management and Reporting of Adverse Events/Adverse Reactions	Pediatric & Malignancy	As per the Protocol Guidance
P15-776	01/09/2015			Change from area study to affiliate study
P15-776	01/10/2015			Revise based on GMA-RC's comments
P15-776	02/23/2016			Revise based on new standard language, legal and investigators' comments
P15-776	08/07/2017	3.0 Responsible parties	Staff revised	Revised based on changes
P15-776	08/07/2017	6.0 Milestones	Timeline change	Revise based on enrollment progress
P15-776	08/07/2017	9.1 Study design	Sample size from 200 to 52	Revise based on enrollment progress
P15-776	08/07/2017	9.2 Setting	Sample size from 200 to 52	Revise based on enrollment progress
P15-776	08/07/2017	9.5 Study Size	Sample size reduced from 200 to 52 with power reduced to 80%; dropout rate reduced to 10%; remove WPAI as key factor for	Revise based on enrollment progress

			sample size	
P15-776	08/07/2017	9.2.3~12.7	Remove “IMS” or change “IMS” to “AbbVie” at appropriate places.	AbbVie is in charge of study operation.
P15-776	08/07/2017	12.5 Risks	Combine 12.5 and 12.6 and add subject insurance language.	Affiliate provides product liability insurance for PMOS.
P15-776	08/07/2017	Annexure	Remove all annexures and CRF.	Annexures not applicable for China. CRF is in a separate document.

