9.2 Setting

The study will take place in China with multiple centers. The study sites will be identified and selected by AbbVie. The study population shall comprise of male and/or female patients who are attending a routine clinical visit and meet all of the inclusion criteria and none of the exclusion criteria. Overall, approximately 52 subjects with clinically diagnosed RA are planned to be enrolled in the study at up to 16 sites.

The recruiting investigators will select potentially eligible patients from consecutive visits within their clinic based on the inclusion and exclusion criteria (Section 9.2.1 and Section 9.2.2). It is the responsibility of each physician to ask every consecutive patient who meets the inclusion criteria of the study to participate to avoid selection bias, and if investigators hold different types of clinics (e.g. routine visit clinics versus emergency clinics), only patients visiting their routine clinics will be used for patient selection. Site personnel should thoroughly assess the eligibility criteria and evidence of this should be stored with the source documentation at site.

Where there is any deviation from the inclusion/exclusion criteria, the patient should be excluded from the study.

9.2.1 Inclusion Criteria:

Patients meeting all of the following inclusion criteria at baseline will be included:

1. Subject has a diagnosis of RA as defined by the 1987 revised ACR classification criteria and/or the ACR/ the European League against Rheumatism (EULAR) 2010 classification criteria (any duration since diagnosis)
2. Male or female subjects \geq 18 years of age who is in compliance with eligibility for adalimumab based on the local label
3. Patients with moderate to severe RA defined as DAS28 (ESR) or DAS28 (CRP) $>$ 3.2
4. Biologically treatment naïve and initiated adalimumab at baseline visit, as per standard daily clinical practice
5. Availability of clinical data of the previous 12 weeks prior to baseline
6. Ability to self-complete patient questionnaires

7. Patients have signed the authorization (or informed consent where applicable) to disclose and use personal health information after been prescribed with adalimumab.

Additional Inclusion Criteria

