9.5 Study Size

Approximately 52 patients diagnosed with RA will be recruited. The planned sample size provides 80% power for detecting a statistically significant improvement in HAQ-DI (Δ HAQ-DI < 0) assuming a mean Δ HAQ-DI of -0.21 and a standard deviation of 0.5 (reference 11), at two-sided significance level of 0.05 and accounting for a 10% dropout rate. The sample size also provides 99% power for detecting a statistically significant clinically meaningful improvement in HAQ-DI (Δ HAQ-DI < -0.22) assuming a mean Δ HAQ-DI of -0.5 and a standard deviation of 0.7, at two-sided significance level of 0.05 and accounting for a 10% dropout rate.

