### **3. STUDY DESIGN**

#### **3.1 Overview of Study Design**

This study is designed as a prospective, observational study to assess the effect of adalimumab on health-related QoL and work productivity in patients with RA in China in clinical practice.

This study is non-interventional. Patient therapy is not decided by the study protocol but falls within current medical practice, and the prescription of adalimumab is clearly separated from the decision to include the patient in this study. The subjects/investigator will follow the current clinical practice in each site and also the routine clinical follow up as determined by the treating physician.

RA patients will be recruited from within the clinical settings of each rheumatologist participating in the study. Approximately 55 patients diagnosed with RA that meet the inclusion and exclusion criteria will be enrolled at up to 8 sites in China.

To assess health and disability outcomes, the HAQ DI will be assessed at baseline, Week 12 and Week 24 after treatment initiation with adalimumab. In addition, other PROs of work activity and well-being, including the WPAI, EQ-5D-3L, and SF-36,

will also be collected. All above instruments have been validated for the Chinese version.

The patients identified by the recruiting investigators based on the study selection criteria will complete a set of patient questionnaires on QoL, functioning, work productivity, treatment satisfaction, impression of change and HCRU. Data will be captured at baseline (D0), Week 12 and Week 24.

The HCRU will also be collected. This includes surgical procedures, hospitalizations, bed days in hospital, physician consultations etc. Costs will be assigned based on the HCRU using standardized costs for each participating centers.

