### **3.2 Study Population**

Approximately 55 patients diagnosed with RA will be recruited from totally up to 8 sites. All eligible patients within the enrollment period will be included; inclusion and exclusion criteria for the population are as below.

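### SAP Section 4 promises about 100 patients and 80% power for work time lost; the planned 52–55 patients give about 43–46%, and 100 is below the section's own 2 × 58 = 116

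*SAP*

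**What the plan says.** The two documents give three enrolment figures.

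- SAP Section 4: "Approximately 100 patients diagnosed with RA will be recruited". It asks for 52 subjects for HAQ DI and 58 for an improvement of 9.9 ± 25 hours of work time lost, each at two-sided 0.05 and 80% power. Because about half the patients may no longer be working, "approximately twice this number (100 patients) will be required to achieve the required number of respondents". Assumed dropout is 13%, from a range of 10–15%.
- SAP 3.1: "Approximately 55 patients diagnosed with RA that meet the inclusion and exclusion criteria will be enrolled at up to 8 sites in China". SAP 3.2 repeats it: "Approximately 55 patients diagnosed with RA will be recruited from totally up to 8 sites".
- Protocol 9.5: "Approximately 52 patients diagnosed with RA will be recruited", with 10% dropout and power stated for HAQ DI only. Protocol 9.2 adds that "approximately 52 subjects with clinically diagnosed RA are planned to be enrolled in the study at up to 16 sites".

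The protocol's amendment log (5.0) explains the gap. It records a cut in sample size from 200 to 52, with "dropout rate reduced to 10%; remove WPAI as key factor for" sample size. The SAP's document history lists only Sections 2 and 5 as changed since its first issue.

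**The concern.** Section 4 is where a reader looks for what the study can detect. It describes a study about twice the size of the one planned elsewhere, and it gives 80% power for a work outcome that the protocol no longer sizes on. Its step from 58 to 100 also does not follow from its own sentence.

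Work productivity is part of the stated objective, and payers are among the intended readers. Someone relying on Section 4 would read a null work-productivity result as the outcome of an adequately powered comparison, when the planned numbers make a miss about as likely as a hit even if the assumed effect is real.

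**Working it through.** **Inputs.** From SAP Section 4: mean change 9.9 h, SD 25 h (the ± is read as an SD, which is an assumption), two-sided alpha 0.05, power 0.80, half working, dropout 13% (range 10–15%). From Protocol 9.5: HAQ DI mean change −0.21, SD 0.5, dropout 10%. Planned enrolment: 52 (protocol) or 55 (SAP). The comparison is within patient, so the one-sample (paired) formula applies.

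**Step 1. Reproduce the SAP's 58 and 52.** Normal approximation: n = ((1.960 + 0.842) / d)² = 7.849 / d², then divide by 1 − 0.13 = 0.87.

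- Hours: d = 9.9/25 = 0.396; n = 50.05; 50.05/0.87 = 57.5, so 58.
- HAQ DI: d = 0.21/0.5 = 0.42; n = 44.49; 44.49/0.87 = 51.1, so 52.

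Both figures reproduce, and both already contain the 13% dropout. Neither is an error.

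**Step 2. The doubling.** 2 × 58 = 116. The stated 100 matches 2 × 50.05 = 100.1, twice the number before dropout. The dropout allowance was lost in the doubling. Because 58 already includes dropout, 116 is the full enrolment figure and should not be inflated again.

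**Step 3. Power for hours lost at each enrolment.** Evaluable workers = N × 0.5 × 0.87. Power is for a paired t-test (noncentral t) at d = 0.396, with the normal approximation alongside.

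| Enrolled | Evaluable workers | Paired t | Normal approx. |
|---|---|---|---|
| 52 | 22.6 (22 to 23) | 42.6–44.3% | 45.9–47.6% |
| 55 | 23.9 (23 to 24) | 44.3–46.0% | 47.6–49.2% |
| 100 | 43.5 (43) | 71.8% | 73.8% |
| 116 | 50.5 (50) | 78.4% | 80.0% |

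**Step 4. Sensitivity for 52–55 enrolled.**

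- 15% dropout with 52 enrolled: 52 × 0.5 × 0.85 = 22.1, so 22 workers and 42.6%.
- 10% dropout with 55 enrolled: 55 × 0.5 × 0.90 = 24.75, so 25 workers and 47.6%.
- No dropout: 26 and 27 workers give 49.3% and 50.9%.

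Every variant stays far below 80%.

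**Step 5. HAQ DI with 52 enrolled.** 52 × 0.87 = 45.2 and 52 × 0.90 = 46.8. Paired-t power at d = 0.42 is 78.7% for 45 and 80.5% for 47, so the protocol's claim of about 80% stands at its own 10% dropout.

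**Step 6. What is sized against what is analysed.** Section 4 sizes hours lost. SAP 5.4 analyses percent overall work impairment and percent activity impairment. Neither document gives an expected change or SD for either score, so their power cannot be computed. Activity impairment is scored as Q6/10 (SAP 3.5.1) and does not require employment, so the halving does not apply to it.

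**The case against.** The strongest reply is that this is un-updated text of limited consequence. The protocol claims no power for WPAI, and its log records that WPAI was removed from the sizing. The latest SAP version (30 May 2019) is dated after the planned end of data collection (30 June 2018), so a correction changes no enrolment and no primary result. The study report will show the actual numbers. That limits the weight of the point, but Section 4 is current SAP text and still states a size and a power that the plan does not have.

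A second reply concerns the headline figure. The SAP's 80% is a normal-approximation figure, while 43–46% comes from a paired t-test. On the SAP's own method the range is about 46–49%. This is a fair qualification, though it does not change the conclusion. The power also belongs to hours lost, which is not a planned analysis variable, and the SAP allows a signed-rank test in place of the t-test. It should therefore be read as a test of Section 4's own claim and not as the power of the WPAI analyses.

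A third reply is that asking for 95% confidence intervals cuts across SAP V0.4, which replaced them with quartiles where normality is violated. SAP 2.2 still allows the mean with its interval, and Protocol 9.7.5 specifies it. The request is incidental to the fix.

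Finally, HAQ DI power falls to 77.7% with 44 evaluable at 15% dropout. The 79–80% quoted here covers the two dropout rates the documents adopt, 10% and 13%. It says nothing about how many patients will in fact stay on treatment.

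**Conclusion.** The concern holds. Section 4's 100 patients contradict the 55 in SAP 3.1 and 3.2 and the 52 in the protocol, and fall 16 short of the section's own 116. With 52–55 enrolled, power for hours of work time lost is about 43–46% by paired t-test, against 80% stated. This rests on 25 being an SD, half of patients working, and 13% dropout. The range widens to 43–48% across 10–15% dropout. No power can be stated for the WPAI scores actually analysed. The primary HAQ DI sizing is essentially unaffected. This should be corrected, but it does not threaten the primary analysis.

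**What to change.** - Rewrite SAP Section 4 on the Protocol 9.5 HAQ DI basis: mean change −0.21, SD 0.5, two-sided 0.05, about 80% power.
- Delete the figure of 100 and the work-time-lost sizing.
- State that the WPAI analyses are not powered. Keep the planned paired tests and report the changes with 95% confidence intervals as in Protocol 9.7.5.
- Reconcile patients (52 or 55), sites (approximately or up to 16, or up to 8) and dropout (10% or 13%) between protocol and SAP, and quote the agreed figures in SAP 3.1, 3.2 and 4.

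The cost is a text revision of the SAP and one reconciliation with the protocol. No patients are added and no test is dropped. The downside is that the stated position on work productivity becomes less favourable.
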